NON-INTERVENTIONAL (NI) STUDY PROTOCOL

Study information

Title	Evaluation of the effectiveness of additional risk minimisation measures (aRMMs) that aim to reduce the risks of phototoxicity, squamous cell carcinoma (SCC) of the skin and hepatic toxicity in patients receiving voriconazole in the Saudi Arabia.	
Protocol number	A1501110	
Protocol version identifier	1.0	
Date	16 August 2024	
EU Post Authorization Study (PAS) register number	EUPAS1000000266	
Active substance	Voriconazole; Triazole and tetrazole derivatives ATC code: J02AC03	
Medicinal product	Vfend® (Voriconazole)	
Research question and objectives	 Vfend® (Voriconazole) The overall objective of the study is to evaluate the effectiveness of the additional risk minimisation measures (aRMMs) being implemented across Saudi Arabia to mitigate the risks of phototoxicity, squamous cell carcinoma (SCC) of the skin and hepatic toxicity with the use of voriconazole. Specifically, the objectives of this research are to: 1 Assess HCPs' awareness of the RM tools (ie, HCP Checklist, HCP Q& Brochure and Patient Alert Card). 2 Assess HCPs' utilization of the RM tools (ie, HCP Checklist, HCP Q& Brochure and Patient Alert Card).` 3 Assess HCPs' knowledge of the risks of phototoxicity, SCC of the skin, and hepatic toxicity with voriconazole. 4 Assess whether HCPs' self-reported practices with respect to minimising the risks of phototoxicity, SCC of the skin, and hepatic toxicity are in accordance with voriconazole SPC.¹ 	
Country of study	Kingdom of Saudi Arabia	

This document contains confidential information belonging to Pfizer. Except as otherwise agreed to in writing, by accepting or reviewing this document, you agree to hold this information in confidence and not copy or disclose it to others (except where required by applicable law) or use it for unauthorized purposes. In the event of any actual or suspected breach of this obligation, Pfizer must be promptly notified.

1. TABLE OF CONTENTS 2. LIST OF ABBREVIATIONS......5 3. RESPONSIBLE PARTIES......7 5. AMENDMENTS AND UPDATES......8 7. RATIONALE AND BACKGROUND......8 8. RESEARCH QUESTION AND OBJECTIVES9 9. RESEARCH METHODS10 9.9. Strengths and Limitations of the Research Methods......20

10.3. Participant withdrawal	24

2. LIST OF ABBREVIATIONS

Abbreviation	Definition
AE	Adverse Event
AEM	Adverse Event Monitoring
CIs	Confidence Intervals
DCT	Data Collection Tools
DCE	Data Check Edits
DSU	Data Safety Unit
EMA	European Medicines Agency
HMA-EMA	Heads of Medicines Agencies - European Medicines Agency
GEP	Good Epidemiological Practice
GPP	Good Pharmacoepidemiology Practices
GVP	Good Pharmacovigilance Practices
HCPs	Healthcare Professionals
HSCT	Hematopoietic stem cell transplant
IA	Invasive Aspergillosis
IEA	International Epidemiological Association
IEC	Independent Ethics Committees
ID	Identifier
IRB	Institutional Review Board
ISPOR	International Society for Pharmacoeconomics and Outcomes Research
ISPE	International Society for Pharmacoepidemiology
IT	Information Technology
LFTs	Liver Function Tests
МАН	Marketing Authorization Holder
NIS	Non-Interventional Study

Abbreviation	Definition
PASS	Post-Authorisation Safety Studies
PRAC	Pharmacovigilance Risk Assessment Committee
Q&A	Question & Answer
RDG	Random Data Generation
RM	Risk Minimisation
RMP	Risk Management Plan
aRMM	Additional Risk Minimisation
aRMMs	Additional Risk Minimisation Measures
SAP	Statistical Analysis Plan
SCC	Squamous Cell Carcinoma
SFDA	Saudi Food and Drug Authority
SPC	Summary of Product Characteristics
SOPs	Standard Operating Procedures
SPF	Sun Protection Factor
URL	Uniform Resource Locator
YRR	Your Reporting Responsibilities

4. ABSTRACT

Refer to ANNEX 1.1 Abstract.

5. AMENDMENTS AND UPDATES

None.

6. MILESTONES

Milestone	Planned date
Start of data collection	15 November 2024
End of data collection	15 February 2025
Registration in the HMA-EMA Catalogues of RWD Studies	10 November 2024
Final study report	30 June 2025

7. RATIONALE AND BACKGROUND

Voriconazole (Vfend®) is a broad spectrum triazole antifungal agent used in the treatment of a range of serious fungal infections in both inpatient and outpatient settings. The clinical benefit of voriconazole has been demonstrated for the treatment of invasive aspergillosis (IA), candidemia in non-neutropenic patients, fluconazole-resistant serious invasive Candida infections (including *Candida krusei*), and serious fungal infections caused by *Scedosporium* spp. and *Fusarium* spp. for which voriconazole is authorised for use in the Saudi Arabia. Voriconazole is also indicated in Saudi Arabia for the prophylaxis of invasive fungal infections in high risk allogeneic hematopoietic stem cell transplant (HSCT) recipients.

Phototoxicity, squamous cell carcinoma (SCC) of the skin, and hepatic toxicity have been designated as important 'identified' risks with administration of voriconazole in the Risk Management Plan (RMP) and are currently described in the Summary of Product Characteristics (SPC). To ensure that these risks are adequately managed, additional risk minimisation measures (aRMMs) across Saudi Arabia have been implemented in February 2023. These included updating the voriconazole SPC¹ with revisions to information on hepatotoxicity, phototoxicity, and SCC of the skin (routine risk minimisation activity), and developing a comprehensive educational programme at the point of patient care, intended to educate/remind healthcare professionals (HCPs) about the risks and how to manage them. These aRMMs target specialty care physicians who prescribe voriconazole (i.e., infectious disease physicians), and clinical pharmacists who manage the drug and its interactions (hereafter referred to as "HCPs"). The details of the Risk Minimisation (RM) tools for the education programme and how these tools are being implemented in Saudi Arabia are described in the RMP. The three components of the RM tools are the HCP Checklist, HCP Question & Answer (Q&A) Brochure, and Patient Alert Card. A brief description of each follows:

- HCP Checklist for the risks of phototoxicity, SCC of the skin and hepatic toxicity: This is the core RM tool that reminds HCPs about: i) the risks of phototoxicity, SCC of the skin, and hepatic toxicity with the use of voriconazole, ii) the appropriate use of voriconazole and management of patients with underlying hepatic impairment and those developing hepatic injury during voriconazole therapy as described in the SPC, iii) the dermatological examination and liver function monitoring required per the SPC, iv) discussing the importance of monitoring these risks with patients, and, v) providing the Patient Alert Card (described below) to each patient prescribed voriconazole. The HCPs have been instructed to complete the HCP Checklist for all new patients receiving voriconazole and retain it in the patient's medical record.
- HCP Q&A Brochure for the risks of phototoxicity, SCC of the skin and hepatic toxicity: This brochure in Q&A format provides detailed information to HCPs about: i) the risks of phototoxicity, ii) counselling patients regarding the risks of hepatotoxicity and SCC of the skin, iii) alerting patients/caregivers to the signs and symptoms that warrant contacting the doctor immediately, iv) regular dermatological examination and liver function monitoring as described in the SPC, v) discontinuing voriconazole if premalignant lesions or SCC are identified; and, vi) providing the Patient Alert Card to patients prescribed voriconazole. This brochure also provides information about the HCP Checklist and Patient Alert Card and instructs HCPs how to use these tools when managing patients receiving voriconazole.
- Patient Alert Card for the risks of phototoxicity and SCC of the skin: The purpose of this wallet-sized folded card is to help remind patients about the need for dermatological evaluations on a regular basis (if phototoxic reactions occur). It also prompts the patient to report phototoxic symptoms that increase the risk of SCC of the skin. Furthermore, patients are reminded to avoid exposure to sunlight, to use protective clothing and sunscreen with high sun protective factor (SPF), and to inform their physicians if they develop sunburn or severe skin reactions or skin abnormalities. The HCPs were instructed to fill in their contact details on the card and give a card to each patient undergoing treatment with voriconazole.

This non-interventional study is designated as a post-authorization safety study (PASS) and is a commitment to Redacted

8. RESEARCH OUESTION AND OBJECTIVES

The overall objective of the study is to evaluate the effectiveness of the aRMMs being implemented across Saudi Arabia to mitigate the risks of phototoxicity, SCC of the skin, and hepatic toxicity with the use of voriconazole.

Specifically, the objectives of this research are to:

1 Assess HCPs' awareness of the RM tools (ie, HCP Checklist, HCP Q&A Brochure and Patient Alert Card).

- 2 Assess HCPs' utilization of the RM tools (ie, HCP Checklist, HCP Q&A Brochure and Patient Alert Card).`
- 3 Assess HCPs' knowledge of the risks of phototoxicity, SCC of the skin, and hepatic toxicity with voriconazole.
- 4 Assess whether HCPs' self-reported practices with respect to minimising the risks of phototoxicity, SCC of the skin, and hepatic toxicity are in accordance with voriconazole SPC.¹

9. RESEARCH METHODS

This section presents methods that will be employed to evaluate the effectiveness of the aRMMs in Saudi Arabia.

9.1. Study design

This is a non-interventional, cross-sectional study to evaluate the effectiveness of RM tools for voriconazole. The study objectives will be accomplished by means of a cross-sectional, web-based survey of all HCPs who were targeted to receive the aRMMs and self-report as prescribers of voriconazole within 12 months preceding the survey in Saudi Arabia (Central, East and North regions). The study aims to obtain completed surveys from 10 HCPs. Data will be collected until 10 completed surveys are obtained or up to a data collection period of 60 to 90 days as a maximum. The data from the HCPs will be collected using a structured self-administered questionnaire to gather evaluation metrics related to the utilization and understanding of RM tool content and messages. In addition, the survey will assess behaviors, including a set of hypothetical scenarios for HCPs. The survey is not intended to be a mechanism for collecting adverse events (AEs), nor is it intended to result in minimizing the numbers of AEs reported. HCPs will be invited by e-mail to participate in the survey and asked to complete the online questionnaire.

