9.2. Setting

The target population will include all HCPs who were targeted to receive Vfend® aRMM materials within 12 months preceding the survey.

At the time of protocol writing, approximately to HCPs were prescribing/dispensing voriconazole in Saudi Arabia and around of these targeted to receive the RM tools in-person, per Pfizer Inc.'s Distribution List. Given this relatively small pool of HCPs, an empirical sample size of 10 HCPs is proposed.

HCPs recruitment and survey will be conducted by the following process:

- HCPs will be invited to participate in the survey by email and/or phone. An email
 invitation will include a web link directing to a webtool named 'Decipher', where the
 survey questionnaire will be available. In the invitation, the survey background and
 objectives, the contact information for questions will be explained to the HCPs.
 Instructions detailing the survey requirements will be displayed at the start of the
 survey.
- If the HCPs agree to participate in the survey, they can access the survey and the instructions for the web questionnaire by clicking on the email link.
- If the questionnaire is not completed in the first attempt, HCPs will receive a reminder email and/or phone (first reminder) 1 week after the initial invitation.
- If the web questionnare remains incomplete, a second reminder will be sent about 2 weeks after the initial invitation.
- If the questionnaire still remains incomplete, a third (and final) reminder will be sent 3 weeks after the initial invitation.

An HCP will be considered unreachable if he/she has been contacted up to 3 times without an answer. For each recruited HCP, the number of times the HCP is contacted, as well as the date and time when he/she completes the web questionnaire, will be recorded. HCP recruitment will be competitive.

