9.4.1. Data Collection Process

Eligible HCPs (those HCPs to whom the RM tools were distributed by hand) will receive a letter by E-mail inviting them to participate in the survey. The invitation letter will include: an overview of the rationale for the survey, reminder about the educational materials, the secure URL to be copied and pasted into their browser, and a unique user identifier (ID). The survey data collection will be open until 10 completed surveys are received, up to 60-90 days. The survey start date begins within 12-18 months after initiation of distribution (05 February 2023) of the aRMMs tools in the Saudi Arabia.

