9.5. Study Size

At the time of protocol writing, a total of HCPs (distribution list shared with Saudi Food and Drug Authority [SFDA]) are expected to initiate or manage patients on Vfend®. All HCPs who were targeted to receive the RM tools (per Pfizer Inc.'s Distribution List.) within the 12 months preceding the initiation of the survey will be invited to participate in the survey. Given this relatively small pool of HCPs, an empirical sample size of 10 HCPs is proposed. Data will be collected until 10 completed surveys are obtained or up to a data collection period of 60 to 90 days as a maximum. It is important to note that the final survey sample size will depend on HCPs' willingness to participate in the survey.

An a priori threshold of 80% correct responses per risk question will be used to define the success of the program. However, this criterion will not be used for formal statistical testing. The selection of this threshold for success was regarded as being subjective and not based on prior knowledge, experience, or established scientific criteria.

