- HCPs with completed questionnaire (C): HCPs who complete the entire questionnaire and submit it.
- Contacted HCPs: HCPs who are contacted by phone or who receive a web link to the online survey via email = C+P+R+F.
- HCPs who agree to participate: HCPs willing to participate in the survey (e.g., by clicking on the link provided in the invitation email) = P+C.
- The HCPs participation in the survey will be examined as follows:

Response rate =
$$\frac{C}{C+P+R}$$

Refusal rate =
$$\frac{R}{C+P+R}$$

The details of analysis will be provided in the SAP.

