9.9.2. Limitations

1. Bias

Selection bias

a) HCPs survey

The potential for selection bias of HCPs participating in a survey is an inherent limitation to any study based on volunteer participation. For instance, it is possible that HCPs willing to

participate in the study will have the highest awareness of risks associated with use of voriconazole.

Non-response bias may also be introduced into the study if targeted HCPs have activated filters in their mailbox that block spam and unsolicited emails. If a very strict degree of message filtering is set, they may not even see the invitation to participate in the survey. Having multiple email addresses could also be a critical situation. If the one used is not the primary address or if the HCPs do not check their emails frequently, they will not receive the invitation during the recruitment period. Some HCPs who are sent a letter may not receive it. This is one of the reasons why the HCPs will also be contacted by phone.

Selection and non-response bias will be assessed by comparing select characteristics between survey non-responders and responders using descriptive statistics, and will be included in the final study report.

Information bias

Recall bias may lead to an underestimation of the HCP recalling having received aRMMs. To mitigate the risk of recall bias for HCPs, they will be recruited in the survey if they have provided (prescribed or dispensed) voriconazole in the past 12 months.

Moreover, web surveys may promote social desirability bias, which refers to the tendency of HCP to give socially desirable/expected responses instead of choosing those reflecting their current knowledge or behavior, e.g., physicians can copy-paste information gathered online instead of giving their own opinions. Social desirability can affect the validity of survey research findings, but the use of prepopulated items in the questionnaire could/tends to reduce this bias. The access to the web questionnaire interface will be strictly limited to the invited participants, with the possibility to participate only once, and a traceability system. Thus, stakeholder bias (multiple answers of people who have a personal interest in survey results and/or who incite peers to fulfill the survey in order to influence the results) or unverified respondents (when it is not possible to verify who responds) are not applicable.

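### Every listed HCP is invited but the survey closes at the 10th completed questionnaire; if that cap is reached, the response rate reflects list size and solicited answers are lost

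*Protocol*

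**What the plan says.** Section 9.5 says that all HCPs targeted to receive the tools in the 12 months "preceding the initiation of the survey will be invited to participate in the survey". It gives the basis for the number: "Given this relatively small pool of HCPs, an empirical sample size of 10 HCPs is proposed". The pool size cannot be read in the public text.

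Section 9.1 sets the stopping rule: "Data will be collected until 10 completed surveys are obtained or up to a data collection period of 60 to 90 days as a maximum". Sections 9.4.1 and 9.5 and Annex 1.1 repeat it; Section 9.4.1 reads "The survey data collection will be open until 10 completed surveys are received, up to 60-90 days".

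Section 9.2 schedules reminders at one and two weeks and then: "If the questionnaire still remains incomplete, a third (and final) reminder will be sent 3 weeks after the initial invitation". No section requires this cycle to finish before closure, or says that questionnaires after the tenth are accepted.

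Section 9.7 defines four outcomes: completed (C), partial (P), failed screening (F) and not participating (R). R pools explicit refusal with no response. Contacted HCPs are C+P+R+F, and "Response rate" is C/(C+P+R). There is no category for an HCP who had not yet answered when the survey closed.

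Section 9.9.2 allows that HCPs willing to "participate in the study will have the highest awareness of risks associated with use of voriconazole", and plans a descriptive comparison of responders with non-responders. It does not mention the cap or early closure.

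**The concern.** A cap on completes makes sense when each further respondent costs recruitment effort. Here everyone on the list is invited anyway, so stopping at ten saves no invitations. It only refuses answers already asked for.

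If the cap ends collection, three things are at stake:

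- **Who is analysed.** The sample is the ten quickest completers, while the endpoints in Section 9.1.1 are proportions of targeted HCPs.
- **What the participation figures mean.** HCPs cut off by closure fall into R together with refusers and true non-responders. The response and refusal rates, and the responder/non-responder comparison, then no longer describe non-response.
- **Precision.** Annex 1.5 turns the results into verdicts at 80% of HCPs. Ten answers support such a verdict poorly, and the rule forbids having more.

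**Working it through.** There is no calculation to reproduce: the figure of 10 is called empirical. The inputs from the protocol are the cap of 10, the invitation of all listed HCPs, reminders at weeks 1, 2 and 3, and the rate formulas of Section 9.7. Pool size N, response speed and true success are assumptions, shown as ranges.

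**1. Response rate once the cap is reached.** If all N listed HCPs are contacted, C+P+R+F = N, so C+P+R = N−F. With C = 10 the response rate is 10/(N−F). For F = 0:

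| N | 15 | 20 | 30 | 50 | 100 |
|---|---|---|---|---|---|
| Capped response rate | 67% | 50% | 33% | 20% | 10% |

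With no cap and a response probability of 0.20 per contact over four contacts, the expected rate is 1−0.8⁴ = 59% for every N. The capped figure varies with list size; the uncapped one does not.

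**2. Is the cap reached, and before the third reminder?** With response probability w per contact, the chance of at least 10 completes after k contacts is P(Bin(N, 1−(1−w)ᵏ) ≥ 10). Before the third reminder k = 3; after the full cycle k = 4.

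| N | k=3, w=0.10 | k=3, w=0.20 | k=4, w=0.10 | k=4, w=0.20 |
|---|---|---|---|---|
| 15 | 0.2% | 13% | 1% | 37% |
| 20 | 2% | 55% | 11% | 85% |
| 30 | 28% | 97% | 62% | about 100% |
| 50 | 91% | about 100% | 99% | about 100% |
| 100 | about 100% | about 100% | about 100% | about 100% |

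The cap is a remote event for a pool of 15 with slow response, and close to certain for a pool of 50.

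**3. Effect on the estimate if speed and awareness are linked.** Assume N = 30, each HCP independently successful with probability 0.60, exponential response times at 0.30 per week for successful and 0.15 for other HCPs, and the link open for 5 weeks. Expected completes with no cap are 18×(1−e^−1.5) + 12×(1−e^−0.75) = 14.0 + 6.3 = 20.3, of which 14.0/20.3 = 69% are successful. Simulation gives:

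| Analysed | Mean estimate | Chance of reaching 80% |
|---|---|---|
| First 10 completes | 72% | 45% |
| Random 10 of all completes | 69% | 35% |
| All completes (about 20) | 69% | 15% |

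The random ten removes speed selection while keeping the sample at ten. Of the 30-point gap, 45−35 = 10 points are speed selection and 35−15 = 20 points are the smaller sample. If speed is unrelated to success (0.20 per week for all), the mean does not shift, but the chance of reaching 80% is still 17% with ten answers against 4% with all completes.

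A second model assumes true success of 50% and response of 0.30 against 0.10 per contact. It gives 69–70% with no cap and 71%, 73%, 75% and 75% with the cap for N = 20, 30, 50 and 100. The cap adds about 1 to 6 points to a volunteer bias of about 20.

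**4. Precision.** The exact 95% confidence interval is 44% to 97% for 8/10 and 56% to 94% for 16/20.

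**The case against.** **The cap may never be reached.** The protocol calls the pool relatively small and says that the final number depends on willingness to take part. Under the rates in step 3 of the working, the cap is reached in about 20% of runs for N = 12, 65% for N = 15 and nearly always for N of 20 or more. If the time limit ends collection, the reminders run in full and the response rate is ordinary. This stands, and it makes every consequence conditional.

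**The direction of bias is not in the document.** A reader might infer from Section 9.9.2 that the fastest responders are the best informed. That section speaks of willingness, not speed, and the 2:1 ratio has no source. This also stands.

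**The 45% against 15% contrast is mainly sample size.** A reader might take it as the size of early-responder bias. The random-ten comparison shows that only about a third of it is.

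**Safeguards exist.** Section 9.2 records the number of contacts and the completion time, Section 9.9.2 plans the responder comparison, and the 80% threshold is not formally tested. A report could also state that collection closed at target, so calling the response rate uninterpretable without condition goes too far. But these measures cannot separate HCPs cut off by closure from true non-responders, and they cannot recover answers that were never collected.

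**Recruitment wording.** Section 9.2 adds "HCP recruitment will be competitive". It is tempting to read this as confirming first come, first counted. The term is not defined and may mean only that there are no quotas, so nothing here rests on it.

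**Conclusion.** The point holds conditionally. Inviting the whole list and closing at ten completes is a poor pairing. If the cap is reached before the time limit, which is likely unless the pool is very small or response is slow, the sample is the ten fastest completers. The reminder cycle may be cut short, and the response rate becomes about 10/(N−F). These consequences follow from the protocol's own rules and need no assumption about awareness.

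Bias in the endpoints does need such an assumption. Where it holds, the added bias is modest: about 3 points in the main illustration and 1 to 6 in the second, and none if speed is unrelated to awareness. The larger and more certain loss is precision. The documents do not support saying that the cap will be reached, or that it necessarily favours a success verdict through selection. A later analysis plan cannot repair the problem, because the rule fixes which questionnaires exist.

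**What to change.** In Sections 9.1, 9.4.1, 9.5 and Annex 1.1, replace the stop-at-ten rule with one fixed closing date within the 60 to 90 day window, set so that every invited HCP has had the full reminder cycle. Count from the last first invitation, since the soft launch in Section 9.8 may stagger them. Analyse all completed questionnaires and describe 10 as a minimum target, not a cap. R in Section 9.7 then means what it says.

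The full cycle needs a single definition: Section 9.2 gives an invitation plus three reminders, while Section 9.4.2 gives at most three invitations in total. Reconcile the two.

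The cost is protocol wording, a slightly longer field period and a few more web questionnaires. No extra invitations are needed, and the three-week cycle fits easily within the planned 15 November 2024 to 15 February 2025. If the cap would not have been reached anyway, the change costs nothing.
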